Primary tumor control was modeled as a function of dose by logistic regression model. A one-sided test with a significance level of 0.05 was employed, which is appropriate for a Phase II proof-of-concept trial. The right column of Figure 13.2 (below) assesses the power of the test of the null hypothesis that  $P(\text{primary tumor control}) < 0.7$  at the chosen target dose. For all the simulations, it was assumed that  $p_l = P(\text{primary tumor control} | \text{dose level})$  increased linearly in the regression model between 60% of  $p_9$  at the lowest level, and  $p_9$ , where  $p_9$  is graphed on the lower axis (for instance, trials labeled 0.9 indicated  $P(\text{primary tumor control})$  increased linearly from 0.54 at Level 1 to 0.9 at Level 9, and equaled  $p_6 = 0.83$  at the true target dose). It is seen that, for the (DLT-td) trials, where the most efficacious dose has acceptable toxicity, the power exceeds 80% when  $p_9$  is 0.89 or greater, but that estimated power is more modest for the DLT+ or DLT++ simulations, where the selected target dose, and hence the efficacy at that dose, is lower. For example, with the DLT+ simulations, level 6 was the most frequently selected target dose (~ 40%), while dose levels 8 and 9 were uncommon (~4.5% and ~1.0%) This is an appropriate outcome, because these would be trials where adequate efficacy can only be achieved at unacceptably toxic doses.

**Figure 13.1:** Operating characteristics for observed toxicity and selection of target dose from simulated trials. Inset describes hazard function. DLT-td, DLT+, and DLT++ are specified in Table 13.1. Asterisks indicate true target dose.

**(4/12/12) Figure 13.2:** Distribution of doses and power functions for simulated trials  
 Hazard function changes from top to bottom as in Figure 13.1. DLT-td, DLT+, and DLT++ are specified in Table 13.1 Left column indicates the expected number of patients treated at each dose, while the right-hand column indicates the power to test the null hypothesis that  $P(\text{primary tumor control}) < 0.7$  at the target dose, as the  $P(\text{primary tumor control})$  at Level 9 increases from 0.7 to 0.99 (see Section 13.2.3 for a more detailed description).

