### **13.5 Analysis Plan**

#### **13.5.1 Analysis of the Primary Endpoints (8/20/10)**

All patients evaluable per Section 13.3 will be used in the DLT analysis (the primary endpoint of the phase I portion), which will be performed after they have been potentially followed for the 1 year observation period. The patients treated at the MTD of SBRT will be used to estimate the 2-year primary tumor control rate (the primary endpoint of the phase II portion), which will be performed after they have been potentially followed for 2 years. Patients not evaluable will be reported separately. For each such patient, the reason for exclusion, protocol treatment received, and toxicities reported during the first year will be listed.

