**13.5.1.2** 2-year Primary Tumor Control Rate at MTD (8/20/10)

Primary tumor control is the absence of local progression (defined as local enlargement confirmed by PET or biopsy which occurs within 2 years from the start of treatment). Marginal failures, which are mentioned in Section 11.3.3, will be considered events for local progression. Distant metastases from the index lung cancer or a second primary tumor are not considered local progression. Patients who die with lung cancer but no documented local progression will be considered non-failures and will be censored on the day of their death. Patients who die without progressive lung disease and have no documented local progression will be considered non-failures and will be censored on the day of their death. Cumulative incidence method will be used to estimate the 2-year primary tumor control rate at the MTD of SBRT. Using this confidence interval, the null hypothesis that the probability of 2-year primary tumor control at the selected target dose (MTD) is 0.7 or less will be tested. Ninety percent confidence interval for the probability of response will be constructed by bootstrapping.

**13.5.2** Analysis of Secondary Survival Endpoints

**13.5.2.1** Progression-Free Survival and Overall Survival (8/20/10)

The same patients used for DLT analysis will be used in these analyses, which will be performed after they have been potentially followed for 2 years. The failure event for progression-free survival (PFS) is defined as the first occurrence of local and/or regional disease progression, distant metastases, second primary tumor, or death due to any cause. Time to PFS is measured from the date of randomization to the date of the failure event for PFS. Overall survival (OS) time is measured from the date of randomization to the date of death due to any cause.

Kaplan-Meier estimation will be used to calculate OS and PFS rate at each radiation dose level. Cox proportional hazards regression will be used to characterize PFS and OS as a function of dose. As in the analysis of 2-year primary tumor control, possible confounding baseline demographic or clinical variables will be included in the regression model if there is evidence of significant imbalance between doses.

**13.5.2.2** Local Progression, Regional Failure, and Distant Metastases

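### The phase II power above 80% and the 5% level in 13.2.3 were derived for a logistic dose-control model, but 13.5.1.2 plans a different test, in MTD patients only, for which neither figure was derived

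*Protocol*

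**What the plan says.** **Design (13.2.3).** "Primary tumor control was modeled as a function of dose by logistic regression model". On the error rate: "A one-sided test with a significance level of 0.05 was employed". On power, for the DLT-td trials: "where the most efficacious dose has acceptable toxicity, the power exceeds 80% when" control at Level 9 (p9) "is 0.89 or greater, but that estimated power is more modest" in the two more toxic scenarios. The null is control below 0.7 at the chosen target dose. In the worked example, control "increased linearly from 0.54 at Level 1 to 0.9 at Level 9, and equaled" 0.83 at Level 6, the target dose in the DLT+ scenario.

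**Analysis (13.5.1 and 13.5.1.2).** "The patients treated at the MTD of SBRT will be used to estimate the 2-year primary tumor control rate". The estimator is cumulative incidence at 2 years, and a null of 0.7 or less is tested from a confidence interval: "Ninety percent confidence interval for the probability of response will be constructed by bootstrapping". No dose term appears.

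**Secondary endpoints (13.5.2.1).** For progression-free and overall survival: "As in the analysis of 2-year primary tumor control, possible confounding baseline demographic or clinical variables will be included in the regression model". Section 13.5.1.2 contains no such model.

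**The concern.** A dose-control model borrows information from every dose level to estimate control at the MTD. A rate computed only in patients treated at the MTD does not. The number of those patients is random: 13.4.2 says that numbers per dose cannot be stated in advance, and no minimum at the MTD is set. So the power and level stated for the first method need not hold for the second.

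This is not a detail left to a later analysis plan. The protocol fixes both methods, and they differ. At stake is the hypothesis test of the phase II primary endpoint: its stated chance of success and its stated false-positive rate were not worked out for the test that is planned.

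**Working it through.** **Inputs from the protocol.** 75 evaluable patients and 2 entries per month (13.3). TITE-CRM with a logistic model, intercept 3, prior N(1, 0.3), weight u/12, start at Level 5, one-level escalation and 12 months of cumulative observation (13.4). Toxicity probabilities from Table 13.1. MTD is the dose with estimated DLT probability closest to 0.20 (13.5.1.1). Control rises linearly from 0.6 × p9 at Level 1 to p9 at Level 9 (13.2.3).

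**Assumptions.** Flat DLT hazard (the trial's own assumption in 13.2), percentile bootstrap, a Wald test in the logistic model fitted to all 75 patients, and full 2-year follow-up. With full follow-up the MTD rate is a simple proportion. The control curve was tried as linear in probability and linear in logit. Runs had 1,000 and 2,250 simulated trials.

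**Step 1: reproduce the plan.** In DLT-td the median is 11 DLTs (protocol range starts at 11), 92% of trials have fewer than 15 (protocol: over 85%), and 8-13 patients fall at each of Levels 5-8 (protocol: 7-14). In DLT+ Level 6 is selected in 43% of trials (protocol: about 40%). Logistic power at p9 = 0.89 is 78.2-78.6% (probability-linear) or 82.0-85.8% (logit-linear). The stated 80% reproduces within 2 points, so it belongs to the logistic model.

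**Step 2: planned test, same design.**

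| DLT-td | Logistic model | MTD-only bootstrap |
|---|---|---|
| Power, p9 = 0.89, probability-linear | 78.2-78.6% | 69.6-70.4% |
| Power, p9 = 0.89, logit-linear | 82.0-85.8% | 71.1-74.4% |
| Rejection rate, p9 = 0.70 | 3-5% | 7-9% |

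With true control exactly 0.70 at whichever dose is selected, the bootstrap level is 8.2%. The number at the MTD has a median of about 28-30 and quartiles of about 16 and 43. It is below 10 in about 14-17% of trials. Slower accrual (75 patients over 48 months) leaves bootstrap power at 70-74%.

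**Step 3: where the level goes wrong.** With x of n patients controlled, the percentile bootstrap rejects when the 5th percentile of Bin(n, x/n)/n exceeds 0.7. Let r be the smallest such x. The level is P(X ≥ r) at 0.70 and the power is P(X ≥ r) at 0.89.

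| n at MTD | Bootstrap r | Level | Power | Exact r | Level | Power |
|---|---|---|---|---|---|---|
| 5 | 5 | 16.8% | 56% | cannot reject | – | – |
| 15 | 13 | 12.7% | 78% | 14 | 3.5% | 50% |
| 20 | 18 | 3.5% | 62% | 18 | 3.5% | 62% |
| 25 | 21 | 9.0% | 87% | 22 | 3.3% | 71% |
| 30 | 26 | 3.0% | 77% | 26 | 3.0% | 77% |
| 35 | 29 | 6.5% | 92% | 30 | 2.7% | 82% |
| 40 | 33 | 5.5% | 93% | 34 | 2.4% | 86% |

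The level moves up and down with n. With no failures every resample equals 1.0, so the lower limit is 1.0 and the null is rejected at any n. At true control 0.70 that happens with probability 0.7^n: 0.7^5 = 16.8%, 0.7^8 = 5.8%, 0.7^14 = 0.7%.

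**Step 4: worked value at Level 6.** Level 6 lies 5/8 of the way from Level 1 to Level 9.
- Linear in probability: 0.54 + (5/8)(0.90 − 0.54) = 0.765.
- Linear in logit by level: 0.160 + (5/8)(2.197 − 0.160) = 1.433, and 1/(1 + e^−1.433) = 0.807.

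Neither gives 0.83.

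**The case against.** **A 90% interval is the right match for a one-sided 5% test.** Nominally it is. The excess comes from the percentile bootstrap on a small, discrete sample. The protocol does not name the type of bootstrap, and an analysis plan could. The 7-9% therefore rests on an assumption. The mismatch between the simulated and planned tests does not.

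**More than 75 patients may contribute.** Section 13.3 lets patients who are not evaluable for DLT into the final tumor control analysis, weighted by observation time. If all 94 entries counted in full, bootstrap power would be about 77-81%, close to the stated figure. Because of the weighting this is an upper case, and the level would still be too high.

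**Power holds when the top dose is chosen.** In DLT-td, Level 9 is selected in about 68% of trials, and bootstrap power there is about 83%. That stands, but at a level of about 7.5%, and the claim in 13.2.3 is not limited to those trials.

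**Stronger readings that the documents do not support.**
- A reader might infer that power collapses below 60%. Such figures belong to an exact test, which the protocol does not plan, or to non-flat hazard shapes whose details are in figures not shown.
- A reader might infer that the bootstrap always inflates the error rate. At n = 20 and n = 30 it stays below 5%.
- A reader might conclude that the Level 6 value must be 0.765. The protocol says linear in the regression model, which also allows the logit scale.
- A reader might conclude that a small MTD group leaves almost no phase II answer. Section 13.5.8 also plans 2-year control estimates per dose level.

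**Conclusion.** The point holds. The stated level and power belong to a logistic dose-control model; the planned test is an MTD-only rate with a bootstrap interval, and the protocol gives no operating characteristics for it. Under flat hazard, 75 patients, a percentile bootstrap and full follow-up, the planned test loses about 8 to 11 points of power against the logistic test (70-74% against 78-86%). It runs at a true one-sided level of about 7-9% on average, with wide variation by the number at the MTD. The loss is moderate, not a collapse, and could shrink if many of the 94 entries contribute.

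The covariate reference in 13.5.2.1 is a plain inconsistency. The 0.83 at Level 6 is a separate slip or an unstated scale. It concerns the DLT+ example and does not affect the DLT-td power claim.

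**What to change.** Choose one of two routes in 13.5.1.2.

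1. **Make the simulated analysis the primary test:** a logistic dose-control model fitted to all treated patients and evaluated at the MTD, with the MTD-only rate as supportive. Cost: the result relies on the assumed shape of the dose-control curve.
2. **Keep the MTD-only test,** with a level-controlled interval (for example exact or complementary log-log), and restate its power and level in 13.2.3. Cost: lower stated power, about 56-60% at p9 = 0.89 for an exact test under the same assumptions. A stated minimum number of patients at the MTD would help, since an exact 5% test cannot reject with 8 or fewer (0.7^8 = 5.8%).

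Under either route, reconcile the 13.5.2.1 reference with the chosen analysis. Recheck the Level 6 value, stating the scale and the matching figure: 0.765 if linear in probability, about 0.81 if logit-linear by level. The work is a wording change and, for the second route, a re-run of the existing simulation.

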### **13.3 Sample Size (8/20/10)**

This trial will accrue 75 patients fully evaluable for the DLT toxicity analysis.

Monte Carlo simulation was used to assess the operating characteristics of this design. Complete trials (2,250 for each trial scenario considered) were simulated using 3 different assumptions about the true probabilities of dose-limiting toxicity at each dose: 1) as assumed; 2) somewhat more toxic than assumed; 3) more toxic than assumed with significant increase in toxicity between doses 6 and 7. Among the operating characteristics considered in the sample size were the expected number of dose-limiting toxicities, the probability of selecting the correct dose (that associated with a 20% probability of DLT) as the target dose at the end of the trial, the time required to complete the trial, and the number of patients treated at or near the target dose. Sample sizes from 30 to 120 were evaluated, as were different rates of patient accrual. A sample size of 75 patients was determined to have acceptable probability of correctly selecting a dose with acceptable toxicity and enough patients treated about the target dose for characterization of the efficacy endpoints, while being feasible for completion of accrual within 4 years.

A patient is fully evaluable for toxicity analysis if:

1. The patient fails to complete treatment due to a DLT.  
OR
2. The patient receives all five RT fractions of the protocol treatment.  
AND
  - A. Experiences a DLT within 1 year from the initiation of treatment  
OR
  - B. Is observed per protocol for 1 year after the initiation of treatment and does not experience a DLT

Patients who complete protocol treatment but have progressive disease and no DLT within 1 year are still considered at risk for a DLT even if they receive chemotherapy. It is not likely that the addition of chemotherapy will greatly affect the occurrence of a SBRT-related DLT, and we did not want to exclude patients at risk of DLT.

A patient who does not complete protocol treatment because of non-protocol, treatment-related toxicity; non-protocol, treatment-related death; or refusal to complete protocol treatment will not be evaluable.

Patients who complete protocol treatment but cannot be observed for a DLT for 1 year (e.g., due to death from other than toxicity or patient refusal) will not count towards the accrual goal, but their data will be used to allocate doses to subsequent patients and in the final analyses for toxicity, primary tumor control and survival, they will be weighted, as appropriate, by the proportion of the observation period they have completed. Note: Patients, who have experienced a DLT, are fully weighted.

It is anticipated that average accrual will be 2 patients per month. Based upon RTOG 0236 (another RTOG trial utilizing SBRT), it is projected that 80% of patient entries will be evaluable for DLT analysis. So to accrue 75 evaluable patients, a total of **94 patients** will have to be entered, and this will take 4 years to complete.

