**Image-Guided Therapy Center (ITC)**

**ATTN: [name]**

**[name]**

**St. Louis, MO 63108**

**[contact]**

**[contact]**

**13.0 STATISTICAL CONSIDERATIONS**

**13.1 Study Endpoints**

**13.1.1** Primary Endpoint of Phase I Portion (7/27/10)

The maximal tolerated dose (MDT) of SBRT radiation dose associated with a 0.20 probability of dose-limiting toxicity (DLT); DLT is defined as any grade 3 or worse toxicity (per CTCAE, v.4, MedDRA, v. 12.0), that occurs within 1 year from the start of SBRT, is possibly, probably, or definitely related to treatment, and is related to the following specific symptoms:

- Grade 3-5 Cardiac Disorders
  - Pericardial effusion
  - Pericarditis
  - Restrictive cardiomyopathy
- Grade 4-5 Gastrointestinal Disorders
  - Dysphagia
  - Esophagitis
  - Esophageal fistula
  - Esophageal obstruction
  - Esophageal perforation
  - Esophageal stenosis
  - Esophageal ulcer
  - Esophageal hemorrhage
- Grade 3-5 Nervous System Disorders
  - Brachial plexopathy
  - Recurrent laryngeal nerve palsy
  - Myelitis
- Respiratory, Thoracic, and Mediastinal Disorders, Grade 3-5, except as noted below
  - Atelectasis (grade 4-5 only)
  - Bronchopulmonary hemorrhage
  - Mediastinal hemorrhage
  - Pleural hemorrhage
  - Tracheal hemorrhage
  - Bronchial fistula
  - Pulmonary fistula
  - Bronchopleural fistula
  - Tracheal fistula
  - Hypoxia (provided grade 3 is worse than baseline)
  - Bronchial obstruction
  - Tracheal obstruction
  - Pleural effusion
  - Pneumonitis
  - Pulmonary fibrosis

- Changes in Pulmonary Function Tests per the SBRT Pulmonary Toxicity Scale (see Section 6.9.5), Grade 3-5
  - FEV1 decline
  - Forced Vital Capacity decline
- Any Grade 5 adverse event attributed to treatment

All reported serious adverse events (SAEs) listed above will be reviewed by 1 of 3 designated senior radiation/medical oncologists who have expertise in the treatment of lung cancer and who are not associated with this study within 2 business days of receipt of all supporting documentation. The determination of those SAEs as a study DLT will be made by the designated independent reviewer. All reported SAEs listed above will be considered DLTs until reviewed by the designated independent reviewer.

**13.1.2** Primary Endpoint of Phase II Portion (8/20/10)

Two-year primary tumor control rate at the MTD of SBRT (See Section 11.3.3)

**13.1.3** Secondary Endpoints

**13.1.3.1** Progression-Free Survival (see Section 11.3.3);

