### **13.4 Allocation of Participants to Doses**

#### **13.4.1 The Weighted Dose-Toxicity Model**

Doses will be allocated to patients by means of the Time-to-Event Continual Reassessment Method (TITE-CRM) Phase I trial. A logistic dose-toxicity model was used for this trial with rescaled dose  $d = (\log(p_0 / (1-p_0)) - 3)$ .

$$p(d) = e^{3+ad} / (1 + e^{3+ad}), \text{ (eq. 1)}$$

In the logistic dose-toxicity model, the prior distribution of the dose-toxicity parameter  $\alpha$  is Gaussian with mean 1 and standard deviation of 0.3 which is based upon experience with other trials using this model.  $\alpha=1.0$  represents our initial assumption about the toxicity of treatment, as displayed in the third column of Table 13.1

The weight function reflects the amount of information available from a patient. If a DLT is observed, the full information from this patient is available and the weight will be 1. Otherwise, the uniform weight function ranging from 0 to 12 months will be used. Each patient will be followed for DLT until the patient either reaches one year (12 months) from the start of SBRT without experiencing a DLT or experiences a DLT, whichever comes first. Let the time to a DLT of patient be  $U_i$ , then the weight function,  $w(u) = u/12$ .

This is translated into the following:

- A) Patients who have enrolled in this trial but have not experienced a DLT have a weight equal to the proportion of the 12 months observation period they have completed.
- B) Patients who have experienced a DLT before 12 months from the start of SBRT or complete protocol treatment without a DLT have a full weight, 1.

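### Section 13.3 makes a first-year DLT non-evaluable if the patient stopped SBRT early for another reason, so it leaves the final MTD analysis although 13.1.1 counts it and 13.4.1 weights it fully

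*Protocol*

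**What the plan says.** Protocol 13.3 gives two routes to full evaluability. The first is "The patient fails to complete treatment due to a DLT". The second requires all five fractions and then either a DLT within 1 year or a full year of DLT-free observation. A later paragraph says that patients who do not complete because of certain toxicities or deaths, "or refusal to complete protocol treatment will not be evaluable". It makes no exception for a DLT that follows.

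Section 13.5.1 carries this into the primary analysis: "All patients evaluable per Section 13.3 will be used in the DLT analysis". Other patients are reported separately, with the reason for exclusion, the treatment received and first-year toxicities.

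Three sections set no completion condition:

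- 13.1.1 defines a DLT as a listed, treatment-related event within 1 year of the start of SBRT. The list ends with "Any Grade 5 adverse event attributed to treatment".
- 13.4.1 (B) says "Patients who have experienced a DLT before 12 months from the start of SBRT or complete protocol treatment without a DLT have a full weight," and sets that weight at 1. The first half of that sentence matters here: any first-year DLT has full weight.
- 13.4.1 (A) says in part "Patients who have enrolled in this trial but have not experienced a DLT have a weight equal to the proportion of the 12 months observation". This makes no distinction between full and partial courses.

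Section 11.3.4 continues follow-up and data collection after treatment is discontinued.

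**The concern.** Take a patient who receives three or four fractions and refuses the rest, or who stops for a treatment-related toxicity that is not a DLT. Grade 3 esophagitis is an example, since 13.1.1 counts listed gastrointestinal events only at grades 4-5. Some months later, within the year, this patient has a listed, related event of DLT grade. The event is observed, is a DLT by 13.1.1, and moves dose allocation under 13.4.1. When the MTD is fixed, 13.3 and 13.5.1 remove it.

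The phase I answer is the dose whose estimated P(DLT) is closest to 0.20. Section 13.2.1 expects a median of only 11 to 18 DLTs among 75 patients, so one or two events can change the level chosen. Early stopping may also be related to the risk of a later DLT, in which case the exclusion is informative.

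**Working it through.** **Reproducing the plan's figures.** Section 13.3 sets the target, "This trial will accrue 75 patients fully evaluable for the DLT toxicity analysis", and says "it is projected that 80% of patient entries will be evaluable for DLT analysis". So 75 / 0.80 = 93.75, rounded up to 94, as stated. At 2 per month, 94 / 2 = 47 months, about 4 years, as stated.

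The design in 13.4 was also coded (eq. 1, normal prior with mean 1 and SD 0.3, one-level escalation, 12 months of cumulative observation, flat hazard, 250 runs). Under DLT-td it gave a median of 11 DLTs, 88% of trials with fewer than 15 and 99.6% with fewer than 18, and chose Level 9 most often. This agrees with 13.2.1 and 13.2.2.

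**Tracing the patient through the text.** Route 1 fails because the DLT did not cause the stop. Route 2 fails because five fractions were not given, and its DLT condition applies only after that requirement is met. The patient is therefore not evaluable, and 13.5.1 leaves only a listing.

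**What one or two dropped DLTs do.** For each level, d = log(p0/(1 − p0)) − 3 and p = e^(3+αd) / (1 + e^(3+αd)), with p0 from Table 13.1 and α at its posterior mean. The MTD is the level with p closest to 0.20. Assumed data, not in the protocol: 10/10/15/15/25 patients at Levels 5-9 with 1/2/3/4/6 DLTs (16 in all). Dropped patients are taken from Level 9.

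| DLT patients dropped | α | p, Level 7 | p, Level 8 | Closest to 0.20 |
|---|---|---|---|---|
| 0 | 0.919 | 0.194 | 0.229 | Level 7 |
| 1 | 0.931 | 0.185 | 0.220 | Level 7 |
| 2 | 0.943 | 0.176 | 0.210 | Level 8 |

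Check of the first row, Level 7: d = log(0.14/0.86) − 3 = −4.815; 3 + 0.919 × (−4.815) = −1.425; p = 0.194. With 2/2/4/4/8 DLTs (20 in all), Level 6 is chosen (0.191), and three have to be dropped before Level 7 is (0.221).

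Over simulated data sets with assumed patient counts per level, deleting DLT patients moved the selected level up as follows (ranges are across repeated runs):

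| Deleted | DLT-td: moved up | DLT+: moved up | DLT+: ended above the true level |
|---|---|---|---|
| One DLT patient | 11-14% | 24-26% | 11-12% |
| Two DLT patients | 22-23% | 44-46% | 23-24% |

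Under DLT-td none ended above the true level, because Level 9 is both the target and the top level. These figures are conditional on such DLTs occurring.

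**Net effect of the rule.** Section 13.3 also removes DLT-free stoppers, so the fair comparison is with keeping all stoppers. With 10% early stoppers (assumed) among 75 patients, 250 runs each:

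| Stoppers' DLT risk relative to completers | DLT-td: MTD higher / lower | DLT+: MTD higher / lower |
|---|---|---|
| Equal | 6% / 9% | 14% / 12% |
| Doubled | 21% / 0.4% | 46% / 3% |
| Halved | 1% / 17% | 6% / 27% |

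**How many events.** The protocol gives no early-stopping rate. The 94 − 75 = 19 non-evaluable entries allowed for cover every reason. If 5% to 10% of 94 entries stop early (4.7 to 9.4 patients) and their DLT risk lies in the range of 13.2.1 (14.7% to 24%), the expected number of DLTs among them is 4.7 × 0.147 = 0.7 to 9.4 × 0.24 = 2.3.

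**The case against.** **The direction is not fixed.** A reader might infer that the rule biases the MTD upward. The documents do not support that. The rule removes DLT-free stoppers too; at equal risk the shifts roughly cancel, and at halved risk they reverse. Stoppers also received less radiation, which could lower their risk. The upward bias needs stoppers to be at higher risk, which is plausible but not stated anywhere. This objection stands, and it limits the point to a conditional one.

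**The deletion percentages overstate harm.** A reader might take 11% to 46% as the chance of a wrong MTD. They are conditional on dropped DLTs, and under DLT-td every upward move is towards the true level. This also stands.

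**Both rules make a level look safer.** This too might be inferred, but it is not so. Under 13.4.1 a DLT after a partial course counts in full at the assigned level and makes that level look more toxic. Excluding DLT-free stoppers from the final analysis does the same.

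**The events stay visible, and 13.3 says DLT patients are fully weighted.** Section 13.5.1 does list them. But a listing does not enter the estimate, and the full-weight note in 13.3 closes a paragraph about patients who completed treatment, so it does not clearly reach non-completers.

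**Section 13.4.2 reassigns patients treated at a lower level.** Every level in 6.1.2 is a five-fraction course, so a partial course has no clear place under that note.

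**Early stopping may be rare.** Treatment is five fractions over 1.5-2 weeks. This bears on size, and leaves the conflict between sections where it is.

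**Conclusion.** The point holds as a conflict between 13.3 with 13.5.1 on one side and 13.1.1 with 13.4.1 on the other. As written, a genuine first-year DLT in a patient who stopped early for another reason is used for allocation but excluded from the analysis that fixes the MTD. It concerns the phase I primary endpoint and is a stated rule, not detail left for a later plan.

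Relative to counting the event, dropping a DLT patient lowered the estimated P(DLT) by about 0.01 at the upper levels in the worked examples, and two or three dropped events moved the selection by one level. Relative to keeping all early stoppers, the MTD tends to be estimated too high only if stoppers carry more risk than completers. These sizes rest on assumed patient counts, an assumed 10% stopping rate and assumed relative risks.

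The exclusion paragraph in 13.3 is also ambiguously punctuated. A reader might infer that it excludes treatment-related deaths, which 13.1.1 counts as DLTs. The natural reading is toxicity or death unrelated to protocol treatment, so this is a matter of clarity only.

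**What to change.** 1. In 13.3 and 13.5.1, include in the DLT/MTD analysis every patient who received at least one fraction and had a DLT within 1 year of the start of SBRT, whatever the reason for stopping.
2. State one rule for non-completers and use it in both allocation (13.4.1) and the final analysis: a DLT has weight 1, and DLT-free non-completers stay in with their 13.4.1 observation-time weight. Selection then does not depend on outcome.
3. State the dose level at which a partial course is analysed.
4. Add a sensitivity analysis that excludes DLT-free non-completers, as a conservative bound. It should not be the main rule: keeping stoppers with a DLT and giving the others no weight lowered the selected MTD in 13% (DLT-td) and 19% (DLT+) of data sets at 5% non-completion, and in 27% and 39% at 10%, with equal risk assumed.
5. Reword 'non-protocol, treatment-related' in 13.3 as 'not related to protocol treatment'.

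The cost is wording. Follow-up already continues under 11.3.4, and the listed SAEs already go to independent review under 13.1.1. The 94 entries need not change if the 80% evaluable share is kept. The estimated P(DLT) may be slightly less favourable, and partial courses add some dose misclassification.
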